Fenofibrate to prevent Ischemic
Cholangiopathy in Donation after Circulatory
Death liver transplantation (FICsDCD)

NCT05514119

28October2022

The FICsDCD Study

MEGA Award Protocol

Title of the study:	Fenofibrate to prevent Ischemic Cholangiopathy in Donation after Circulatory Death liver transplantation (FICsDCD)
Principal investigator:	[name]
Co-investigator(s):	[name], [name], [name]
Mentor:	[name]
Statistician:	[name]
IRB# or Activity#	22-007122

Abstract

Ischemic cholangiopathy (IC) is an early-onset, progressive bile duct stricturing syndrome occurring in 5-15% of transplanted livers, leading to biliary obstruction and allograft failure in up to 60% of cases. There is no definitive treatment for IC besides re-transplantation. The differential rate of IC drives the global preference for livers donated after brain death, over more abundant livers donated after circulatory death (DCD) that are prone to warm ischemia—the primary precipitant of IC. Any intervention to ameliorate IC will likely improve DCD organ utilization globally, thereby reducing transplant waitlist mortality and morbidity. Toxic bile acids (BA) in stagnant bile cause bile duct injury and stricturing, which may explain why stricturing progresses even after ischemia resolves at transplantation. Peroxisome proliferator-activated receptor (PPAR) agonists (such as the generic oral agent **fenofibrate**) potently down-regulate BA synthesis, promote BA excretion, and are safe and effective in other cholestatic diseases, but are not studied in transplant recipients. We hypothesize that fenofibrate could be safe, effective, cheap, and thus generalizable to impede the IC propagation. **In this prospective pilot study, we aim to evaluate 1) the tolerability and safety, 2) the efficacy of 12 weeks once-daily fenofibrate in reducing IC incidence after DCD liver transplantation, 3) assess the association between serum markers of cholestasis and development of IC.** Tolerability and safety will be assessed as proportions of: drug discontinuation, and new grade 3 or 4 adverse events. Efficacy will be assessed as incidence of cholangiographically-diagnosed IC and incidence of any IC-related complication.

Research Plan

Specific Aims

Specific Aim 1: To assess the tolerability and safety of 12 weeks once-daily fenofibrate (Lofibra) in a LT recipient population

Primary endpoint: Proportion of patients discontinuing fenofibrate due to adverse events

Secondary endpoints:

- a. Proportion of patients with a new grade 3 or 4 adverse event.
- b. Proportion of patients with acute cellular rejection during fenofibrate treatment
- c. Mean change in calculated glomerular filtration rate (eGFR) from baseline during fenofibrate treatment weeks 4, 8, 12, and at 4 weeks after end of treatment
- d. Proportion of patients with myopathy confirmed by serum creatine kinase elevation at weeks 4, 8, 12, and at 4 weeks after end of treatment

The FICsDCD Study

Specific Aim 2: To assess IC incidence after 12 weeks of once-daily fenofibrate (Lofibra) in DCD LT recipients, compared with a historical, untreated control. Treatment and control populations will have an elevated predicted risk of IC, defined as alkaline phosphatase >2.5x upper limit of normal (ULN) at 21-60 days after LT.

Primary endpoint: IC incidence with 12 weeks fenofibrate versus a historical untreated cohort.

Secondary endpoints:

- a. Incidence of any IC-related complication at 12 weeks of fenofibrate treatment as a composite endpoint: biliary intervention (biliary stricture dilation, endoscopic biliary stent placement, percutaneous biliary drain placement), initiation of antimicrobial therapy for cholangitis or biloma, re-transplant evaluation due to IC, or death attributed to IC.
- b. Rate of alkaline phosphatase improvement to <1.67x ULN after 12 weeks fenofibrate.

Specific Aim 3: To assess the association between serum biomarkers and IC development.

Endpoints: Correlation of serum alkaline phosphatase, gamma glutamyl transferase, bile acids, fibroblast growth factor 19 (FGF19) and 7-alpha-hydroxy-4-cholesten-3-one (7AC4) levels at weeks 0, 4, 8, and 12 of treatment, with development of IC at 12 weeks of treatment.

II. Background and Significance

Liver allografts donated after circulatory death (DCD) improve access to liver transplantation (LT) by increasing organ supply. Widespread adoption DCD LT however is hindered by the higher risk of ischemic cholangiopathy (IC) in DCD organs, a progressive biliary structuring syndrome observed within weeks-to-months after LT, which increases morbidity, mortality, and cost by demanding frequent cross-sectional imaging, endoscopic and percutaneous biliary intervention, hospitalization, parenteral antimicrobials, and in almost 60% of individuals, re-transplantation due to allograft failure.¹ Elevated alkaline phosphatase (ALP) at 1 and 2 months are validated early signals of impending IC, but lack of preventative interventions relegate LT centers to manage complications reactively when they arise.²

Rates of IC in livers procured after brain death (DBD) range 1-10%, while DCD IC rates range 10-30%.³⁻⁵ DCD IC rates are better at experienced centers, with Mayo Clinic Arizona (MCA) and Mayo Clinic Florida (MCF), two of the largest DCD LT centers in the US—having a rate of 10-12% (N=20-24/year).¹ Despite this, the risk of DCD IC dissuades most LT centers from entertaining DCD organs. Almost 30% of recovered DCD livers are unused, compared to 7.5% of DBD livers, and despite their greater abundance, DCD livers account for just 8.5% of the transplanted livers in the United States.⁶ Effective interventions against IC may therefore increase DCD liver utilization.

The key histologic features of early IC are biliary endothelial ischemic necrosis and consequent impairment of biliary drainage (choleresis).^{3,5} The duration of liver non-perfusion after donor cardiac standstill (warm ischemia) is the most important risk factor for IC that explains the higher rate of IC in DCD versus DBD livers, with warm ischemia >30 minutes being a standard cutoff for rejecting an allograft offer.⁷ However, warm ischemia time does not explain the often inexorable progression of biliary destruction well after arterial perfusion is re-established at transplantation. This suggests other ongoing injury processes in the transplanted liver, intervening on which could mitigate the downstream complications of IC.

An attractive hypothesis for post-transplant IC progression is the accumulation of bile acids (BA)—hydrophobic molecules with detergent and apoptotic effects on hepatocyte and cholangiocyte lipid membranes—within the biliary tree.^{3,8} The pathologic effects of BA are recognized to the extent that flushing the biliary tree to remove BA is standard at time of organ procurement. The immediate post-transplant period is also marked by low concentrations of bile

The FICsDCD Study

phospholipids which impairs BA micellization, and low concentrations of bicarbonate which impairs bile alkalinization, both of which likely potentiate BA-induced cytotoxicity.³ While the antecedent to IC is impaired choleresis due to bile duct necrosis, it is conceivable that BA stasis propagates injury and/or impairs healing after transplantation. The hypothesized process is therefore a spiral of BA accumulation due to ischemia-induced biliary injury, unopposed BA activity due to lower phospholipid and bicarbonate concentrations, BA-induced cytotoxicity, cytotoxicity-induced biliary injury, and further BA accumulation.

Countering the deleterious effects of BA in IC could draw parallels from the treatment of primary biliary cholangitis (PBC) and primary sclerosing cholangitis (PSC), both of which involve disrupted choleresis and accumulated toxic concentrations of BA. Importantly, unlike PSC and PBC where disease progression is fueled by immune activity, the injury trigger in IC appears to be self-limited; ischemia prior to transplantation. It is reasonable therefore to postulate that pharmacologically reducing BA concentrations in a DCD allograft, beginning soon after transplantation, could impede biliary injury and improve allograft survival.

The peroxisome proliferator-activated receptor (PPAR) agonists bezafibrate and fenofibrate (fibrates), which potently downregulate BA synthesis, activity, and promote choleresis, are promising therapeutics for PBC and PSC.^{9,10} At least 11 prospective trials (including one pivotal trial) in PBC (N=481), and 2 prospective trials in PSC (N=23) have demonstrated their ability to improve ALP, BA, and other disease endpoints over the standard of care.¹¹

While approved for dyslipidemia and used off-label for pre-LT PBC and PSC, fibrate safety or efficacy have not been studied in any transplant population for any indication. Additionally, despite the likely benefits (including cost of \$5-25/month), the known risk profile of fibrates, including nephrotoxicity, hepatotoxicity, and myotoxicity, require study in LT recipients who are prone to these toxicities from immunosuppressives and/or their baseline clinical state.

In this prospective pilot study, our primary aim is to describe the tolerability and safety of 12 weeks of once-daily fenofibrate in a LT population, with efficacy as a secondary aim, and determining associations of cholestasis and bile acid activity biomarkers with IC as a tertiary aim.

We believe this pilot study to have at least four key implications on current post-LT care or in opening new areas of investigation. First, demonstrating fenofibrate tolerability and safety early after LT is useful context of IC but also because both PBC and PSC have a 20% recurrence rate after LT and fenofibrate may be considered for post-LT prophylaxis (current standard of care is universal lifelong ursodeoxycholic acid after LT for PBC, and observation alone after LT for PSC). Second, if an efficacy signal is demonstrated, we will leverage the existing three-site Mayo Clinic collaboration (together the largest transplant consortium by far) to conduct a randomized controlled trial to more conclusively assess efficacy of fenofibrate in preventing IC. Third, we hope to determine if biomarkers besides ALP—a test confounded by other liver processes—are associated with IC and facilitate early detection. Fourth, data gathered may allow us to investigate a predictive scoring model utilizing donor and patient characteristics and these biomarkers.

The FICsDCD Study

III. Progress Report and Preliminary Studies

As two of the largest DCD LT program in the nation, the MCA and MCF transplant hepatology teams including this study's PI and Co-Is are experienced in diagnosing and managing IC. Our group holds a monthly DCD IC Multidisciplinary Conference to review cases and discuss management. Finally, the MCA LT Program has contributed to seminal peer-reviewed papers on the DCD IC syndrome including the recently proposed IC classification system.¹ At present we are developing a dataset of over 300 DCD LT recipients at our center which will be used to identify the historical controls of this study.

IV. Research Design and Methods

Study design: A single-arm, open-label, prospective study of 12 weeks of fenofibrate (Lofibra) 160mg once daily in donation after circulatory death liver transplant recipients who have serum alkaline phosphatase $>2.5 \times$ ULN 21-60 days after transplantation, to determine fenofibrate tolerability, safety, and efficacy in preventing the ischemic cholangiopathy.

Treatment cohort: Recipients of DCD liver transplants at MCA or MCF

Historical cohort: DCD liver transplant recipients at MCA or MCF between 1/1/2016-6/1/2021

Diagnosis of IC: We will utilize previously-published diagnostic criteria for IC, defined as the occurrence of non-anastomotic biliary strictures in the absence of hepatic artery compromise¹

Inclusion criteria:

1. Female or male patients who have undergone DCD LT
2. At least one serum ALP level $>2.5 \times$ ULN between post-LT days 21-60 days (inclusive) after LT.

Exclusion criteria:

1. LT performed for primary sclerosing cholangitis or primary biliary cholangitis
2. Hepatic artery compromise (e.g thrombosis, stenosis), evaluated on abdominal doppler ultrasonography or angiography prior to enrollment..
3. Untreated biliary anastomotic (surgical) stricture or bile leak between days 0-60 after LT, evaluated during routine clinic examinations, labs, and abdominal ultrasonography.
4. Baseline GFR <30 ml/min
5. Previously known intolerance or allergy to fenofibrate
6. Other clinically significant comorbid condition, including psychiatric conditions, which in the opinion of the study team, may interfere with patient treatment, safety, assessment, or compliance with the treatment
7. Adults lacking capacity to consent to treatment

Interventions:

1. Consenting eligible patients will receive the fenofibrate formulation *Lofibra*, 160mg or renally-adjusted equivalent daily. Intended treatment duration of 12 weeks.
2. Post-transplant laboratory monitoring will be per standard Institutional protocol, at least weekly, through treatment period. Study laboratory monitoring will be done as below.

Analyses:

Specific Aim1:

- a. Tolerability: Proportion of patients who discontinue fenofibrate due to adverse event.
- b. Safety:
 - Proportion of patients with a new grade 3 or 4 adverse events based on CTCAE 5.0 Scale

The FICsDCD Study

- Proportion of patients with acute cellular rejection during fenofibrate treatment
- Mean change in eGFR from baseline at treatment weeks 4, 8, 12, and post-treatment week 4
- Proportion of patients with elevated serum CK at weeks 4, 8, 12, and post-treatment week 4

Specific Aim 2:

- a. Efficacy: We will use a two-group design to test whether Group 1 (treatment) proportion (P1) is different from Group 2 (control) proportion (P2) ($H_0: P_1 - P_2 = 0$ versus $H_1: P_1 - P_2 \neq 0$). We will use a two-sided, two-sample Fisher's Exact Test with Type I error rate (α) of 0.05.
- b. Sample size: Allowing a 10% dropout rate, a sample size of 32 in the treatment arm and 116 in the historical control arm (1:4 ratio) will achieve 80% power to detect an IC proportion reduction of 30% in the control arm to 5% in the treatment arm.

Specific Aim 3: Serum biomarker association with IC development: We will use the Wilcoxon Rank-Sum test to compare serum ALP, gamma glutamyl transferase, serum BA, FGF19 and 7AC4 levels at weeks 0, 4, 8, and 12 of treatment, with development of IC at 12 of treatment.

Data management: The study will use REDCap, a secure web platform for building and managing online databases and surveys for electronic data collection. REDCap provides automated export procedures for seamless data downloads to Excel and common statistical packages (SPSS, SAS, Stata, R), as well as a built-in project calendar, a scheduling module, ad hoc reporting tools, branching logic, file uploading, and calculated fields.

Schedule of Events

Procedure	Screening: Post-LT day 21-60	Treatment			Post Treatment
		Weeks 0-4	Weeks 5-8	Weeks 9-12	Week 4
Informed consent	X				
Inclusion and exclusion criteria	X				
Physical examination	X				
Medical history	X				
Intervention: fenofibrate		Daily	Daily	Daily	
Routine Labs*	X	Weekly	Weekly	Weekly	Weekly
Study Labs**	X	Once ^{a,b}	Week 6 ^b	Week 12 ^b	Once ^b
Lab result review		Weekly	Weekly	Weekly	Once
Assess tolerability, safety		Weekly	Once	Once	Once

*Protocol transplant monitoring labs (billed to insurance): total bilirubin, ALP, alanine aminotransferase, aspartate aminotransferase, sodium, potassium, creatinine, eGFR, and complete blood count.

**Study labs per FICsDCD budget: GGT, serum bile acids, CK, FGF19 (ELISA), 7AC4 (LC-MS)

^a collect within 3 days after start of treatment

^b combine with transplant monitoring labs

Study Strengths and Limitations:

The mechanisms of action of PPAR-alpha agonists like fenofibrate predict a strong likelihood of impeding the dreaded transplant complication of IC, yet has not been studied. We propose the first safety and tolerability analysis of fenofibrate in LT recipients. Additionally, we assess the efficacy in reducing IC incidence in a population at increased risk of IC (based on elevated alkaline phosphatase levels at 3-5 weeks after transplant). We proposed fenofibrate as it is readily available and the cheapest PPAR-alpha formulation, at \$5-25/month. Finally, MCA and MCF, as two of the largest DCD LT centers in the nation, makes us uniquely positioned to perform this study, and our existing IC study collaborations in Minnesota and Florida may allow a future multi-center

The FICsDCD Study

randomized controlled trial to more conclusively assess efficacy. Our proposed pilot study is primarily limited by its sample size, owing to a low anticipated IC accrual rate, and the consequent inability to randomize a prospective control arm.

Study Timeline:

Month	0-2	2-4	4-6	6-8	8-10	10-12	12-14	14-16	16-18
Enrolment	X	X	X	X	X				
Treatment	X	X	X	X	X	X	X		
Develop Historical Cohort								X	
Analysis								X	X

V. Human Subjects

Population: The treatment-arm population is 32 adults with decision making capacity, and enrolled from among the MCA and MCF LT recipient population. The control arm is a historical LT recipient population. The study does not involve fetuses, pregnant women, children, prisoners, institutionalized individuals, or others who are likely to be vulnerable.

Research Materials: We will collect, analyze, and biobank blood for study purposes in 32 participants. Participants will receive telephone contact from study coordinators at least monthly during 3 months of treatment, and 1 month after treatment. We will review the electronic medical record of the 32 participants and 116 historical controls including clinical notes, laboratory, imaging, and pathology results, and procedure reports.

Enrolment strategy: Patients who have undergone DCD LT will be screened for eligibility between days 21-60 days after LT. All consecutive LT recipients meeting criteria will be offered enrollment in the study. The historical control cohort will be identified through the Mayo Clinic electronic medical record.

Potential Risks: Fenofibrate has been FDA-approved for dyslipidemia since 2004. The most common serious adverse events (SAEs) reported are elevated liver enzymes (3-13%), headache (3%), abdominal pain (5%), constipation (2%), nausea (2%), back pain (3%), CK elevation (3), and respiratory symptoms (2-6%). Fibrates are also associated with elevated serum creatinine, an important consideration in LT recipients who are concurrently exposed to other nephrotoxic agents and/or may have baseline renal impairment. In a large meta-analysis, mean creatinine increase was 0.37mg/dl, and GFR impact was minimal (2.7 ml/min). Moreover, both returned to baseline after drug cessation.¹² Fibrates are postulated to increase creatinine production, with direct nephrotoxicity occurring to a lesser degree. We will monitor participants with weekly labs and monthly and ad hoc study coordinator calls to determine SAEs. Patient reported intolerance or grade ≥ 3 SAEs (CTCAE 5.0 Scale) attributed to drug will be addressed with temporary or permanent drug discontinuation or dose reduction.

Protection: The primary aim of this study is to determine if the widely-used medication fenofibrate is tolerable and safe after LT, a unique population in which it has not been studied. Particular areas of interest are nephrotoxicity, hepatotoxicity, myotoxicity, and risk of allograft rejection. We use the standard, CTCAE 5.0 scale to determine severity of adverse events. The baseline safety and tolerability profile of fenofibrate is obtained from the FDA and post-marketing ('real world') data reported through LexiComp. As we are intervening early after transplantation, participants will be monitored intensively by the Transplant Program (twice weekly labs and at least twice-weekly transplant coordinator contact) in addition to Study staff.

The FICsDCD Study

Benefits: IC is among the most serious complications after LT. The proposed study of fenofibrate, a medication generally considered safe albeit not studied in a LT population, may facilitate further study of this agent as a low risk, low cost, intervention to impede the development of IC and its downstream complications including frequent biliary intervention, hospitalization, loss of functional capacity, allograft failure, and need for re-transplantation.

VI. Gender/Minority Mix There are no known gender or racial disparities in IC. All eligible, consecutive LT recipients irrespective of gender or race will be offered study enrolment.

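### The severe-event endpoint in Specific Aim 1 stops at grade 4, so a patient whose only qualifying event is fatal is counted as having no severe event

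*Combined protocol and SAP*

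**What the plan says.** The severe-event endpoint is stated three times, each time as a closed range:

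- Abstract: "Tolerability and safety will be assessed as proportions of: drug discontinuation, and new grade 3 or 4 adverse events".
- Specific Aim 1, secondary endpoint (a): "Proportion of patients with a new grade 3 or 4 adverse event".
- Section IV, Analyses, Specific Aim 1(b): "Proportion of patients with a new grade 3 or 4 adverse events based on CTCAE 5.0 Scale".

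Section V, Protection, confirms the grading system: "We use the standard, CTCAE 5.0 scale to determine severity of adverse events".

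The primary endpoint of Specific Aim 1 is "Proportion of patients discontinuing fenofibrate due to adverse events". It does not say how a death on treatment is classified. The remaining Aim 1 endpoints are acute cellular rejection, change in eGFR, and myopathy or CK elevation. Death is named in one endpoint only, the Aim 2 efficacy composite, which ends with "re-transplant evaluation due to IC, or death attributed to IC".

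Section V, Potential Risks, uses an open-ended threshold, but for another purpose: "grade ≥ 3 SAEs (CTCAE 5.0 Scale) attributed to drug will be addressed with temporary or permanent drug discontinuation or dose reduction".

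**The concern.** Tolerability and safety are the primary aim of this pilot, which presents itself as the first such analysis of fenofibrate in liver transplant recipients. The abstract names two measures for that aim, discontinuation and new grade 3 or 4 events. If the second is applied as written, the most serious possible outcome can fall on the side of no severe event.

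The error has one direction: leaving fatal events out can lower the proportion but never raise it. The plan also does not say whether the earlier grades of an event that ends in death are kept. Two reviewers could therefore classify the same death differently, one counting the patient through an earlier grade 3 or 4 record and the other recording only the final fatal grade.

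**Working it through.** **Inputs.** Endpoint range: grades 3 and 4 (abstract; Specific Aim 1; Analyses). Scale: CTCAE 5.0 (Analyses; section V, Protection). Treated patients: 32 (section V, Population), or about 29 after the 10% dropout allowed in the sample size statement (0.9 × 32 = 28.8). The plan gives no expected rate, threshold, test, power or stopping rule for this endpoint, so it has no figure of its own to reproduce.

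**Assumption.** The documents name CTCAE 5.0 but do not define a grade above 4. That this grade is death is taken from the named scale.

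**Step 1: apply the rule to each kind of patient who dies.**

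| Patient | Counted under grade 3 or 4? |
|---|---|
| Separate new grade 3 or 4 event recorded, then a fatal event | Yes |
| Fatal event only | No |
| One event that worsens through grade 3 or 4 to death | Not stated: depends on whether earlier grades are kept |

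**Step 2: look for another endpoint that would count the second patient.**

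- Primary discontinuation endpoint: possible, but the text does not say.
- Rejection, eGFR and CK endpoints: none counts a death as such.
- Aim 2 composite: only if the death is attributed to IC, and then as an efficacy event.

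A death on treatment from any cause other than IC is therefore not explicitly counted by any endpoint.

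**Step 3: size per patient.** Each fatal-only patient left out lowers the proportion by 1/32 = 3.1 percentage points (1/29 = 3.4 with 29 patients).

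Illustration with an assumed count of four patients with events, one of them fatal-only (exact Clopper-Pearson 95% intervals):

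- Fatal event counted: 4/32 = 12.5% (3.5 to 29.0%).
- Rule as written: 3/32 = 9.4% (2.0 to 25.0%).

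**Step 4: chance that the gap matters at all.** The documents give no fatal-event rate, so a range is assumed. If p is the probability that a patient's only qualifying event is fatal, the chance that at least one such patient is missed is 1 − (1 − p)^n.

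| Assumed p | n = 32 | n = 29 |
|---|---|---|
| 1% | 28% | 25% |
| 2% | 48% | 44% |
| 3% | 62% | 59% |
| 5% | 81% | 77% |

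For example, with p = 2% and n = 32, 1 − 0.98^32 = 0.476. These percentages depend entirely on the assumed p and are not predictions for this trial.

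**The case against.** **The intent is obvious and the gap is narrow.** The endpoint is per patient, and participants have at least weekly laboratory tests and frequent contact with the transplant team. Most patients who die may therefore already have a recorded grade 3 or 4 event. This stands as a limit on size: the gap concerns only patients whose sole qualifying event is fatal. It does not remove the gap, because three matching statements of a closed range are the rule an analyst would follow.

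**The endpoint is secondary and descriptive.** This is correct. It is one of four secondary endpoints under Aim 1, with no test or decision attached, and the two illustrative intervals overlap almost entirely. It would be too strong to call it the main safety proportion, although the abstract does name it as one of the two measures of tolerability and safety.

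**Other endpoints may catch deaths.** A fatal event ends treatment and might be counted as discontinuation, and IC-attributed deaths enter the Aim 2 composite. The first is unstated and the second is an efficacy count, so neither corrects the severe-event proportion.

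**A stronger reading that the documents do not support.** A reader might infer that section V, Potential Risks, contradicts the endpoint by using grade 3 and above. It does not. That sentence covers serious events attributed to the drug and says how they are managed, whereas the endpoint covers any new event and says what is analysed. The three statements of the endpoint agree with each other. The wording in section V is context, not a second definition.

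**Merging could hide deaths.** This is a fair point about the remedy, and it is met by reporting the number of deaths separately as well.

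**Conclusion.** The point holds in this limited form: as written, the severe-event endpoint leaves out fatal events, and no other Aim 1 endpoint explicitly counts them. Its effect is 3.1 percentage points per fatal-only patient out of 32, always in the drug's favour.

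A reader might go further and infer that every death is recorded as a non-event. That does not follow, because a patient with a separately recorded new grade 3 or 4 event is still counted.

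The conclusion rests on the grade above 4 being death on the named scale and on applying the range literally. How many patients would be affected cannot be judged from the documents. The defect does not threaten the design and alters no stated figure, but it should be corrected before analysis because safety is the study's primary aim.

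**What to change.** In the abstract, Specific Aim 1 secondary endpoint (a) and Analyses, Specific Aim 1(b), replace grade 3 or 4 with *grade 3 or higher, including fatal events*. Also report the number of deaths on its own line, so that deaths are not absorbed into the combined proportion. The management wording in section V does not need to change for this.

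The cost is wording only: no change to sample size, visits or assays. The reported proportion will stay the same or become slightly less favourable.

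### The muscle-toxicity endpoint (Aim 1, secondary endpoint d) has two conflicting definitions, is scored at weeks that do not match the CK schedule, and omits myopathy that resolves between scored visits

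*Combined protocol and SAP*

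**What the plan says.** Specific Aims, Specific Aim 1, secondary endpoint d: "Proportion of patients with myopathy confirmed by serum creatine kinase elevation at weeks 4, 8, 12, and at 4 weeks after end of treatment".

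Section IV, Analyses, Specific Aim 1, part b (Safety), gives the same endpoint as "Proportion of patients with elevated serum CK at weeks 4, 8, 12, and post-treatment week 4". Myopathy is no longer required. Neither text states a CK threshold, refers to the pre-dose value, or says what to do with a CK result from another date.

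The neighbouring safety endpoints do refer to the pre-treatment state: "Proportion of patients with a new grade 3 or 4 adverse event" and "Mean change in eGFR from baseline at treatment weeks 4, 8, 12, and post-treatment week 4".

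In the Schedule of Events, CK belongs to the study labs ("Study labs per FICsDCD budget: GGT, serum bile acids, CK, FGF19 (ELISA), 7AC4 (LC-MS") and not to the weekly routine panel. Study labs are drawn at screening, once in weeks 0-4 with the footnote "collect within 3 days after start of treatment", at week 6, at week 12, and once after treatment.

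Section V, Potential Risks, describes safety follow-up between these visits: "We will monitor participants with weekly labs and monthly and ad hoc study coordinator calls to determine SAEs". Patient-reported intolerance, or events of grade 3 or higher, "attributed to drug will be addressed with temporary or permanent drug discontinuation or dose reduction".

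**The concern.** Myopathy can begin on any day, but endpoint d looks at four dates. Follow-up between those dates exists to find toxicity and act on it, so a case that is found and managed early is among those most likely to have a normal CK at the next scored visit. It then counts as no event.

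The Analyses wording also allows the opposite error. Nothing in it requires the CK elevation to be new. No exclusion criterion concerns CK, and the screening CK is drawn but not used.

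Section V, Protection, names myotoxicity among four safety areas of particular interest. Safety and tolerability are the primary aim, and the protocol presents this as the first such analysis of fenofibrate in liver transplant recipients. Endpoint d is the only one that yields a myotoxicity proportion, and it could be wrong in either direction.

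**Working it through.** **1. Scored times against scheduled CK draws**

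| Time | Scored for endpoint d | CK scheduled |
|---|---|---|
| Screening | no | yes |
| Within 3 days of starting | no | yes |
| Week 4 | yes | no |
| Week 6 | no | yes |
| Week 8 | yes | no |
| Week 12 | yes | yes |
| 4 weeks after treatment | yes | yes |

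Two of the four scored times have no scheduled CK. Read literally, even a raised CK on the scheduled week 6 draw falls outside the endpoint.

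**2. Denominator.** The plan states no expected rate or precision for endpoint d. Its denominator of 32 comes from the Aim 2 sample size (30% versus 5%, 80% power, two-sided 0.05, 1:4), which reproduces: the continuity-corrected two-proportion formula gives 29 treated and 116 controls, and 29 × 1.1 = 31.9, so 32.

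**3. Expected cases.** Potential Risks gives CK elevation as 3 with no percent sign. Read as 3%, 32 × 0.03 = 0.96 cases. This is a CK-elevation rate; the documents give no rate for myopathy.

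**4. Weight of one patient.** 1/32 = 3.1 percentage points. Exact (Clopper-Pearson) 95% intervals are 0-10.9% for 0/32 and 0.1-16.2% for 1/32.

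**5. Share of cases missed.** Assume onset is uniform over the 12 weeks and CK stays raised for *d* weeks after onset. A case is seen only if a scored draw falls within those *d* weeks.

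- Draws at weeks 4, 8 and 12, as the endpoint names them: missed share = 1 − *d*/4 for *d* up to 4.
- Only week 12 both scored and scheduled on treatment: missed share = 1 − *d*/12 for *d* < 4.

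| *d* (weeks, assumed) | Weeks 4, 8, 12 | Week 12 only |
|---|---|---|
| 1 | 75% | 92% |
| 2 | 50% | 83% |
| 3 | 25% | 75% |
| 4 | 0% | not computed |

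The post-treatment draw adds nothing when *d* < 4, because it comes 4 weeks after the last dose.

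**6. Chance of reporting zero.** With a 3% true rate and a missed share *m*, the probability of 0/32 is (1 − 0.03(1 − *m*))^32. For *m* = 0, 25%, 50% and 75% this is 38%, 48%, 62% and 79%.

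**7. Raised pre-dose CK, Analyses wording only.** If a proportion *b* of patients starts with a raised CK that persists to a scored visit (assumed), the reported proportion is *b* + (1 − *b*) × 0.03. For *b* = 3%, 5% and 10% this is 5.9%, 7.9% and 12.7%, or about 1.9, 2.5 and 4.1 of 32 patients.

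**8. Why a rule for new elevation needs a margin.** Suppose a patient's CK is stable but raised, so that the screening value and the four later scheduled values are exchangeable. The first of five is the highest with probability 1/5, so at least one later value exceeds it with probability 4/5. Counting any rise would label about 80% of such patients as new cases.

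**The case against.** The strongest reply is that little is lost. Discontinuation due to adverse events is the Aim 1 primary endpoint, new grade 3 or 4 events are secondary endpoint a, and neither is tied to fixed visits. A severe case, or one that ends treatment, is therefore reported. Endpoint d is secondary and descriptive, with no hypothesis or decision rule, and the intervals for 0/32 and 1/32 overlap heavily. Fixed visits also give uniform detection: the documents have no rule for ordering an unscheduled CK, and the schedule lists tolerability assessment weekly only in weeks 0-4 and once in each later treatment period.

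Much of this stands and limits the point. A reader might infer several stronger claims that the documents do not support:

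- **That myopathy between visits disappears from the trial.** It does not if it is grade 3 or 4 or leads to permanent discontinuation. The cases lost altogether are lower-grade ones handled by temporary interruption or dose reduction. The protocol does not say whether a temporary stop counts towards the primary endpoint; if it does, the lost group is smaller still.
- **That the endpoint rests on CK alone throughout.** That is the Analyses wording. The Specific Aims wording also requires myopathy, so a raised pre-dose CK without myopathy is not an event there.
- **That every raised pre-dose CK is counted.** It must persist to a scored visit, and it counts through the text's silence, not through a stated rule.
- **That most cases are missed.** This depends on how long CK stays raised, which the documents do not say. With draws at weeks 4, 8 and 12 the missed share is zero once the elevation lasts 4 weeks.

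What the reply does not answer is that the other endpoints give no myopathy proportion, that the two definitions differ, and that the scored weeks and the schedule disagree.

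**Conclusion.** The point holds in a limited form. Endpoint d has two definitions that must be reconciled, and its scored weeks must be reconciled with the CK schedule. As written, it leaves out CK-confirmed myopathy that resolves between scored visits; under the Analyses wording only, it can also count an elevation that predates treatment.

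In absolute terms the effect is about one patient, but fewer than one case is expected, so one patient decides whether the report reads 0/32 or 1/32. That comparison rests on reading the CK figure as 3%. The missed shares rest on uniform onset and an assumed duration of CK elevation, and the inflated proportions on an assumed pre-dose prevalence. The Aim 2 sample size is unaffected. The definition should be corrected before analysis; the point does not threaten the trial's overall safety reporting.

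**What to change.** Use one definition in both Specific Aim 1 and the Analyses section: the proportion of all treated patients with new CK-confirmed myopathy at any time from first dose to 4 weeks after last dose, using any CK result, scheduled or unscheduled.

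- State what counts as myopathy and which CK level confirms it.
- Define new against the screening CK with a pre-specified margin, for example a higher CTCAE 5.0 grade than at screening. Any rise at all is not enough.
- Report the proportion with new CK elevation alone as a separate line.
- Reconcile the endpoint weeks with the Schedule of Events, then give a descriptive by-visit CK table at the visits where CK is actually drawn.

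The new definition needs no extra visit or test: the screening CK is already drawn and participants' medical records are already reviewed. Reconciling the weeks is a text change if the endpoint moves to the scheduled draws; it costs more if draws are moved or added. The statistical downside is that unscheduled CKs follow symptoms, so detection is less uniform than at fixed visits. The by-visit table shows the uniform part.
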